#### **Endpoint / Comparator**

The primary objective of this study is to provide a validation to **ISO 81060-2:2018** for non-invasive blood pressure measurement accuracy for the Vital Detect blood pressure monitor on the intended population. The Vital Detect blood pressure will be compared to the Reference Sphygmomanometer via a modified same arm sequential method with dual auscultators.

The final analysis will contain no fewer than 85 qualified subjects to achieve approximately 255 paired observations. The end goal is to pass the Criterion 1 and Criterion 2 of **ISO 81060-2:2018**.

#### **Criterion 1**

Mean Error of individual paired determinations  $\leq \pm 5.0$  mmHg  
Standard Deviation of determination  $\leq 8.0$  mmHg

#### **Criterion 2**

Standard Deviation of the average paired determinations must meet criteria in Table 1 below (page 12).

#### **Study Population**

The study population for phase 1 will include a minimum of 30 qualified adult subjects. Phase 2 will include a minimum of 55 additional subjects for a total of 85 subjects for the study. The subject or legally authorized representative must understand the study and provide consent for participation by signing the Informed Consent Form. The subject shall also be informed about the clinical investigation within his/her ability to understand

Subject enrollment is based on meeting the inclusion criteria and none of the exclusion criteria and the subject and data demographics needed for the study.

#### **Subject Inclusion to the study:**

- Subjects must be able to provide an informed consent or have legally authorized representative consent to participate.
- Subject must be willing and able to comply with the study procedures.
- Subject must be  $\geq 18$
- Subject or legally authorized representative must be able to read or write in English.
- Subjects with a finger circumference  $< 8.3$  cm
- At least 30% of subjects shall be male and at least 30% of subjects shall be female

#### **Subject exclusion to the study:**

- Lack of Informed consent.
- Subjects with deformities or abnormalities that may prevent proper application of the device under test.
- Subject is evaluated by the investigator or clinician and found to be medically unsuitable for participation in this study.
- Subjects with known heart dysrhythmias

Clinimark [name], USA Site 001	TITLE: Multiparameter Monitor Non-Invasive Blood Pressure Validation Study Clinimark Study ID#: PR2019-329 Principal Investigator: [name]	DOCUMENT NUMBER PR# 2019-329 SHEET 8 of 22	REV 1
---	--	--	-----------------

- Subjects with compromised circulation or peripheral vascular disease.
- Subjects with clotting disorders or taking prescribed blood thinners.
- Subjects that cannot tolerate sitting for up to 1 hour.
- Subject with a blood pressure demographic that has already been filled.

#### **Limb size distribution:**

[figure not shown]
Since this is not a standard cuff configuration, the subjects will only be selected to show a distribution across the range of finger sizes.

#### **Duration of Clinical Investigation**

Each subject, and therefore use of the device, is expected to take up to 1 hour. The study is expected to take approximately 1-6 weeks to complete for this subject population.

### **Modified Same arm Sequential Method**

Equipment Set Up:

#### **Procedure**

1. Set up all equipment prior to start of study.
2. Explain the procedure to the subject. Have the subject or authorized representative read the Informed Consent Form and review the information answering all questions. Once all questions have been answered, have the subject or authorized representative sign the form. Have the subject or authorized representative complete the Health Assessment Short Form. Review the study with the subject or authorized representative to make sure he / she wants to participate. Each subject / representative will be given a copy of the consent form prior to release.
3. Measure the subjects finger circumference and ensure that it within the acceptance criteria and measure the forearm length from the location on the arm where the stethoscope is placed to the base of the index finger and record these values. The forearm length is for reference only.
4. Prepare the subject for the study.
  - 3.1 The subjects should be asked to empty their bladders prior to sitting down.
  - 3.2 The subject will be positioned such that the subject:
    - is seated comfortably with legs uncrossed and feet flat on the floor.
    - has the back, elbow and forearm supported;
    - has the middle of cuff site at the level of the left ventricle of the heart.
  - 3.3 Recommend that the subject be as relaxed as possible and that they avoid talking during the entire procedure.
  - 3.4 The cuff should be applied on the bare arm and there shall be no arm compression proximal to the cuff

Clinimark [name], USA Site 001	TITLE: Multiparameter Monitor Non-Invasive Blood Pressure Validation Study Clinimark Study ID#: PR2019-329 Principal Investigator: [name]	DOCUMENT NUMBER PR# 2019-329 SHEET 9 of 22	REV 1
---	---	---	-------

3.5 Before the first reading is taken, 5 min should elapse.

5. Apply the pulse oximeter to the subject as a secondary review for a regular rhythm and to provide the heart rate values. Apply the 3-lead ECG only if needed to confirm normal sinus rhythm.
6. Record subject initials, subject number and demographics information onto the Case Report Form.
7. Review the Health assessment short form, if the subject meets the inclusion / exclusion criteria to the study then accept into the study, and continue otherwise the subject is considered not enrolled.
8. Record device information for tracking. (manufacturer, model #, serial or lot, hardware / software control info) on the Case Report Form (CRF).
9. Measure the circumference of the upper arm at the midpoint and place the appropriate sized reference blood pressure cuff on the bicep of the subject.
10. Attach the reference sphygmomanometer to the connector hose on the appropriate port on the reference blood pressure cuff.
11. Make sure the observers for the reference sphygmomanometer are positioned at a height level with the center of the manometer and within 15° from the centerline of the mercury tube (if used) so that parallax errors are avoided.
12. Both observers shall make an initial baseline reference blood pressure determination using a dual stethoscope. The last audible Korotkoff sound, fifth phase or K5, will be used for the diastolic blood pressure determination. Record which Korotkoff sound was used on the CRF. Record the baseline reference blood pressure reading on the CRF.
13. Apply the device under test on the subjects finger and follow the Instructions For Use (IFU).
14. Wait at least 60 seconds and then take the initial baseline device-under-test blood pressure determination. A third observer will record the data for the device-under-test and the reference values from the auscultators insuring that no pair differ more than 4 mmHg. These baseline data points shall not be used in the accuracy determination.
15. Make sure the previous reading of the device-under-test is cleared prior to the next reading.
16. For each subsequent blood pressure determination, wait at least 60 seconds between the readings.
17. The observers will start with the reference sphygmomanometer, then device-under-test, alternating until three valid paired blood pressure determinations are completed. The final reading should be on the reference sphygmomanometer. Make sure to wait at least 60 seconds between each of the readings.
18. The reference blood pressure determinations prior to the test device and post the test device will be averaged for the actual reference blood pressure determination of comparison.
19. Record each blood pressure determination and the pulse rate on the Case Report Form.
20. A maximum number of attempts for the subject is 8 paired determinations.
21. After three valid test-reference pairs are completed, the cuff will be removed.
22. The auscultator will monitor the subject's comfort level and the cuff test site throughout the duration of the study and upon removal of the cuff.
23. The subject will be advised during the study that he/she may stop the test at any time.
24. All equipment will be removed from the subject.
25. The observers will record any final notes on the Case Report Form. The subject will be released with no follow-up required.

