**Identification and description of the investigational device**

The devices under test will be built according to the Vital USA design control processes.

The devices will include the Vital USA Vital Detect multiparameter platform with finger cuff.

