**Vital Detect Multiparameter Platform Monitor**

Firmware	Version Number
NIBP (Non-Invasive Blood Pressure) Firmware	V10.0.15-48
Main	V5.0.3-1
Display	V1.0.11-20

Clinimark [name], USA Site 001	TITLE: Multiparameter Monitor Non-Invasive Blood Pressure Validation Study Clinimark Study ID#: PR2019-329 Principal Investigator: [name]	DOCUMENT NUMBER PR# 2019-329 SHEET 4 of 22	REV 1
---	---	---	-------

The Vital Detect blood pressure monitor is an investigational device. Device model numbers, serial numbers, date(s) of use, subject ID number(s) will be recorded on the Case Report Forms. A Device Accountability Log will be maintained for the sponsor's equipment documenting date of receipt, and date of return for used and unused product.

The intended purpose of the test is to evaluate the Vital Detect blood pressure monitor to **ISO 81060-2:2018**. The intended use for these products are manual and automatic Non-Invasive Blood Pressure monitoring on adults age 18 and older.

All appropriate testing has been performed and demonstrates safety and efficacy for use in human studies prior to Clinimark's receipt of the devices. Such documentation resides in the Design History Files at Vital USA. The device under test, the Vital Detect blood pressure monitor with finger cuff, is the only component expected to come in contact with the subjects.

The manufacturing of the device followed the good manufacturing practice regulation as identified in 21 CFR 820.

Instructions for installation, use, storage and handling can be found in the Vital Detect Manual.

Vital USA staff will train the Clinimark staff on the instructions for set up and use of the Vital Detect blood pressure monitor prior to start of the study.

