## **Risks and benefits of the Investigational device and clinical investigation**

Currently the FDA defines blood pressure devices as Class II devices CFR Section: 21 CFR §870.1130, Noninvasive Blood Pressure Measurement System. – Cardiovascular Diagnostic Devices. **The devices under test in this study are thereby considered non-significant risk devices.**

The device and use of the device under test does not meet the definition of significant risk device under 21 CFR 812.3(m)

For the purpose of this study:

It is not intended as an implant.

- The cuff is applied to the bicep and is removed following data collection, typically less than 1 hour

It is not purported or represented to be for use in supporting or sustaining human life

- These devices are not used to support or sustain human life.

It is not used for use of substantial importance in diagnosing, curing, mitigating, or treating disease, or otherwise preventing impairment of human health

- They are not used to diagnose, cure mitigate or treat disease.

The device as used in this investigation does not present a serious risk to the health, safety, or welfare of a subject.

- See below for discussion of risk associated with the device and use of the device.

There are no anticipated risks or adverse device effects to be assessed. There are no contraindications for use in the proposed study / study population (See description of Study Population below). There may be other risks to the subject associated with the device or procedure that are unforeseeable at this time.

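### Does the heart-level instruction, which does not say which of two cuffs it means, leave the device-reference comparison open to a positioning error?

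*Combined protocol and SAP*

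**What the plan says.** The relevant text is in the Procedure under Modified Same arm Sequential Method. Step 4 (its sub-items are printed as 3.1 to 3.5) has the subject seated so that he or she "has the back, elbow and forearm supported" and "has the middle of cuff site at the level of the left ventricle of the heart". Sub-item 3.4 then reads: "The cuff should be applied on the bare arm and there shall be no arm compression proximal to the cuff". At step 9 staff "place the appropriate sized reference blood pressure cuff on the bicep of the subject". Step 13 puts the device under test on the finger and binds the operator to its instructions for use, which Packaging and Labeling describes as separate documents.

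Elsewhere, the identification section states: "The devices will include the Vital USA Vital Detect multiparameter platform with finger cuff". The Vital Detect Multiparameter Platform Monitor section adds that sponsor staff "will train the Clinimark staff on the instructions for set up and use of the Vital Detect blood pressure monitor". The risk section, while arguing that the device under test is not a significant-risk device, says: "The cuff is applied to the bicep and is removed following data collection, typically less than 1 hour". Step 3 records the length from the stethoscope site to the base of the index finger, with the remark: "The forearm length is for reference only".

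**The concern.** There are two cuffs and one height rule, and the rule names neither cuff. The visible text gives no hand or finger height. The risk section places a cuff on the bicep while discussing a device that the rest of the plan places on a finger, so a reader could doubt which cuff the word means.

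The whole result is a device-minus-reference difference judged against fixed limits. If the two sites sit at different heights, a column of blood separates them and the difference picks up a pressure offset. Two routes would turn that into bias:

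- **Finger height uncontrolled.** The instructions for use set no hand position, or staff depart from it, and the device does not compensate.
- **Rule applied to the finger.** The arm cuff is then left off heart level, and the error enters the reference itself.

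In either case a reader of the report could not separate device error from positioning error. The forearm length recorded at step 3 would not help, because it runs along the limb and does not give a vertical distance.

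**Working it through.** The plan states no figure on this point, so the check is mainly a comparison of texts, followed by one sensitivity calculation.

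**1. Which cuff does the height rule mean?** In the order of the Procedure:

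| Step | Content | Cuff in place |
|---|---|---|
| 4, sub-item 3.2 | heart-level rule | none yet |
| 4, sub-item 3.4 | cuff on the bare arm | none yet |
| 9 | reference cuff on the upper arm | arm |
| 12 | baseline reference reading by both observers | arm |
| 13 | device applied to the finger, under its instructions for use | arm and finger |
| 14 | baseline device reading | arm and finger |

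Wherever the Procedure gives a cuff a location, it is the arm (3.4 and step 9). Step 13 refers to the finger device as the device under test and does not call it a cuff. At the first reading the height rule governs, the arm cuff is the only one on the subject. To take the rule as meaning the finger, staff would have to apply it to a site with nothing on it and disregard 3.4, two sub-items later.

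**2. What governs the finger?** Step 13 makes the instructions for use binding, and the sponsor trains the staff on set-up and use. The content of those instructions is not available here, so whether they fix a hand position, and whether the device compensates for height, is unknown. Anything under the Equipment Set Up heading is also not visible.

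**3. What about the bicep sentence in the risk section?** It conflicts with the finger cuff in the identification, monitor and Blood Pressure Cuff sections, and with the finger placement at step 13. It belongs to a regulatory argument about risk class and tells no one how to position a subject.

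**4. How large could an uncontrolled height difference be?** Assumed, and not in the documents: blood density 1000 to 1060 kg/m3, g = 9.81 m/s2, 133.322 Pa per mmHg, no compensation by the device.

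- Offset per cm = density × 9.81 × 0.01 / 133.322
- At 1000: 98.1 / 133.322 = 0.736 mmHg per cm
- At 1060: 103.99 / 133.322 = 0.780 mmHg per cm
- Height equal to the 5.0 mmHg mean-error limit of criterion 1: 5.0 / 0.780 = 6.4 cm, to 5.0 / 0.736 = 6.8 cm
- At 10 cm: 7.4 to 7.8 mmHg

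Table 1 tightens as mean error grows (6.95 mmHg at zero, 4.79 at 5.0), so a smaller offset could also matter. How much smaller depends on a between-subject standard deviation that is not known in advance.

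**5. Does any planned figure depend on the wording?** No. 85 subjects × 3 pairs = 255, as planned, and criteria 1 and 2 are the same on either reading.

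**The case for a change.** The strongest case for acting is that the result is a paired difference, the potential effect is on the scale of the acceptance limit, and the remedy is a few words. The height rule precedes both cuffs, and no later visible step rechecks position once the finger device is on. The plan also uses the word cuff loosely: under Limb size distribution it refers to finger sizes, and step 21 speaks of one cuff when two are in place. A support for elbow and forearm does not by itself bring the hand level with the upper arm.

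The textual part of this stands. The rule names no cuff, no finger height is printed, and the bicep sentence is wrong for a finger device.

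The inference to bias does not follow. It needs either a misreading that 3.4 and the step order both discourage, or a gap in instructions that cannot be seen from here. The sensitivity figures show what an uncontrolled offset would do. They do not show that one will arise. The loose wording at step 21 has no effect, since step 24 removes all equipment. A position check before every reading, or a field for vertical distance, would add work for each subject without altering either criterion.

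**Conclusion.** No change to the plan follows. Followed as written, the arm reference cuff is at heart level and the finger device is used under its own instructions by staff the sponsor has trained. Any pressure offset that remains is then part of how the device performs in use, and it belongs in the measured error.

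The missing cuff name is a gap that trained staff fill sensibly from the neighbouring sub-item and the order of steps. The bicep sentence is a clerical slip in a risk argument. Neither touches the 85 subjects, the 255 pairs, the 5.0 and 8.0 mmHg limits of criterion 1, or Table 1.

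The conclusion assumes that staff read the height rule together with 3.4, and that the instructions for use say how the hand is held or the device allows for it. The second assumption cannot be verified from the documents. If it failed, the exposure would be 0.74 to 0.78 mmHg per centimetre under the assumptions stated above, but nothing in the documents indicates that it does.

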### **Summary Overview**

The Vital Detect blood pressure monitor will be evaluated in two phases, Phase 1 and Phase 2. Phase 1 will consist of 30 subjects that will approximate the distribution of blood pressures as outlined in **ISO 81060-2:2018**. Upon completion of Phase 1, an interim analysis will be performed to determine whether or not to proceed with Phase 2. Phase 2 will test a minimum of 55 additional subjects to achieve a minimum of 85 subjects. The maximum number of subjects enrolled will not exceed 150 subjects.

Two trained observers, typically a Registered Nurse (RN) or Licensed Practical Nurse (LPN), will observe (listen to) the Korotkoff sounds at the brachial artery of the arm. The reference blood pressure measurements by the nurses will be performed sequentially with the device under test. The nurses will complete 1 or 2 initial baseline auscultatory reference blood pressure measurements and device under test measurements. This is followed by 3 to 8 valid paired blood pressure readings of auscultatory reference blood pressure measurements alternated with device under test measurements. For accuracy claims, the test device measurements will be compared to those made by the reference device. The data for the final analysis will contain no fewer than 85 subjects with a minimum of 255 valid paired observations. At least 90% of the subjects will contribute 3 paired observations. In this case, additional subjects shall be used to complete the minimum number of paired observations.

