## **Design of the Clinical Investigation**

### **Method**

The Vital Detect blood pressure monitor will be evaluated as a comparative, single center, non-randomized, study in a minimum of 30 subjects, conducted in 2 phases. The maximum number of subjects enrolled is 150 for both phases, to achieve 85 valid data sets. Each subject test is expected to take up to 1 hour. The overall data collection process is expected to be completed across 6 weeks.

The Auscultator will have a normal audiogram before the study begins. All experimenters will review the protocol prior to test.

Each subject or his/her legally authorized representative will be provided an IRB approved Informed Consent. As applicable, subjects will be told about any new information that might change their decision to participate. Subjects who have completed the informed consent and health questionnaire form and meet inclusion/exclusion criteria will be enrolled in the study if they meet desired blood pressure demographics. The study will be explained within his/her ability to understand.

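### Does accepting subjects at step 7, before any blood pressure is measured, leave the enrolled count and the cap of 150 undefined?

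*Combined protocol and SAP*

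**What the plan says.** Step 7 of the Procedure is where acceptance is recorded: "Review the Health assessment short form, if the subject meets the inclusion / exclusion criteria to the study then accept into the study". For a subject who fails, it adds that "otherwise the subject is considered not enrolled". The exclusion lists in the Synopsis and under Study Population both contain this item: "Subject with a blood pressure demographic that has already been filled".

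Blood pressure is first measured at step 12: "Both observers shall make an initial baseline reference blood pressure determination using a dual stethoscope". The device under test goes on at step 13 and gives its own baseline at step 14.

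Two other sections state who is enrolled. Under Method, subjects who have consented, completed the health form and met the criteria "will be enrolled in the study if they meet desired blood pressure demographics". Study Population bases enrolment on the inclusion and exclusion criteria together with "the subject and data demographics needed for the study".

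The cap appears twice: "The maximum number of subjects enrolled will not exceed 150 subjects" in the Summary Overview, and "The maximum number of subjects enrolled is 150 for both phases, to achieve 85 valid data sets" under Method.

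**The concern.** Read in strict order, step 7 asks for a decision on a criterion that cannot yet be judged from a study measurement. Steps 1 to 6 cover consent, the health form, finger and forearm measurement, positioning, the oximeter and demographics. The Informed Consent Process section bars any procedure before consent, so a screening blood pressure taken earlier is not available either.

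If the category is in practice decided at step 12, a subject turned away there has passed step 7 but does not satisfy the Method section's condition for enrolment. The early termination section ends data collection once a subject is found ineligible, without saying whether that subject had been enrolled.

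The cap counts enrolled subjects. At stake would be how much of the margin above 85 is left for subjects removed by the 12/8 mmHg reference stability rule and for the extra subjects needed when only two pairs are valid. It could also matter whether the cap is reached before the blood pressure distribution is complete.

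**Working it through.** The plan gives no figure of its own on this point. The check is a comparison of the text followed by a short calculation on the cap.

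**1. Order of steps.** Acceptance is at step 7 and the first blood pressure at step 12. The timing gap is confirmed. Step 12 itself, however, contains no category check and no instruction to turn anyone away. That event is an inference: step 12 is simply the earliest point at which a measured category is known.

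**2. Whether step 7 is a single, closed decision.** Eligibility is spread over several steps. Step 3 applies the finger-size limit, and step 5 reviews rhythm, which bears on the dysrhythmia exclusion. The numbering is also not strictly chronological: the sub-items on subject preparation mention cuff application and the wait before the first reading, although the reference cuff is placed only at step 9.

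**3. Enrolment status of a subject whose category is full.**

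| Place | Condition | Status |
|---|---|---|
| Procedure, step 7 | Must meet all criteria, including the filled-category exclusion | Not enrolled |
| Method | Must meet the criteria and the desired blood pressure demographic | Not enrolled |
| Study Population | Must meet no exclusion and fit the demographics needed | Not enrolled |
| Early termination section | Data collection stops on ineligibility | Enrolment not addressed |

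Three places agree and the fourth is silent. To count such a subject as enrolled, one must treat step 7 as passed by someone who met one of its exclusions.

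**4. The cap under each reading.** Inputs from the Method section: at most 150 enrolled and 85 valid data sets.

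- Margin: 150 - 85 = 65 places.
- Natural reading (not enrolled): category exclusions use 0 of the 65.
- Opposite reading (enrolled), no other losses: 85 is out of reach once more than 65 are turned away; 65/150 = 43.3%.
- Opposite reading with an assumed share *l* of the remaining subjects lost for other reasons: largest number turned away = 150 - 85/(1 - *l*), rounded down. At *l* = 5%, 150 - 89.5 gives 60. At 10%, 150 - 94.4 gives 55 (share 1 - 85/135 = 37.0%). At 15%, 150 - 100 = 50.

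The loss rates are assumptions. The documents give no turn-away rate, no category quotas and no share of arrivals per category, so the chance of reaching the cap cannot be estimated from them.

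**5. Effect on the accuracy criteria.** Step 14 excludes the baseline readings from the accuracy determination, and Equations (1) to (6) use only paired determinations. A subject turned away at baseline adds nothing to *n* or *m*.

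**6. Records.** The Case Report Forms section already captures inclusion and exclusion information and the baseline blood pressure. The Trial Master File list includes a Subject Enrollment Log, and the Monitoring Plan has eligibility verified for each subject.

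**The case for a change.** The best case for acting is that this criterion will be used. Phase 1 is to approximate the blood pressure distribution of the ISO standard, so categories will fill and later arrivals will be refused. The monitor must confirm that no exclusion applies, yet the plan names no reading and no time for this one. Two or three sentences would settle it, with no new measurement, and would keep the investigational device off a subject already known to be excluded.

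Part of this stands. The deciding reading is not named, and naming it would be tidy. But the step 12 baseline comes before the device is applied and is the reading staff would naturally use. The Health Assessment Short Form and the standard cannot be seen here; if either already fixes the classifying reading, all that is missing is a cross-reference. Prescribing the baseline would also not be plainly better, since it is not analysed and a subject may fall in another category on the analysed readings.

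The argument about the cap does not stand. It depends on the less natural reading of enrolment and on a high turn-away rate, for which the documents give no support.

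**Conclusion.** The timing gap is real, but it does not make the enrolment rules conflict. A subject excluded for a filled category is most naturally not enrolled and takes no place under the cap of 150, so all 65 spare places remain for other losses. Even on the contrary reading, and with assumed other losses of 0 to 15%, 65 down to 50 subjects could be turned away with 85 valid data sets still attainable. Criteria 1 and 2 do not change, and the records needed to account for these subjects are already provided for.

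The conclusion rests on reading step 7, Method and Study Population together, and on staff using the baseline reference reading or whatever the Short Form or the standard supplies. This is missing detail that a competent site fills without harm, so no change to the plan is called for.
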